The EQ-5D-3L measures HRQoL and consists of two parts. The first part contains five questions about mobility, daily activities, self-care, pain/discomfort, and anxiety/depression [11, 12]. Each question can be answered with no problem (1), some/moderate problem (2) unable to perform certain activities/having extreme problems (3). The answers can be summarized in an index value based on an existing preference-based value set. In this study, the EQ-5D-3L value set by Dolan [13] will be used for the main analyses and a Swedish experience-based value set in a sensitivity analysis [14]. For the EQ-5D-3L index, 1 represents full health and 0 represents a value equal to being dead. EQ VAS measures the persons

Karolinska Institutet – Research protocol: Follow-up with patient-reported outcome measures for improved health related quality of life – Construct validity and responsiveness of EQ-5D-3L in patients with rheumatic disease

health today on a visual analogue scale (VAS) from 0 (worst imaginable health) to 100 (best imaginable health) [11, 12].

Disease activity

DAS28 was developed for patients with RA and contains questions about tender and swollen joints, disease activity and inflammation [15]. DAPSA was developed for patients with PsA and contains questions about tender and swollen joints, disease activity, pain, and inflammation [16, 17]. BASDAI was developed to measure disease activity in patients with AS and contains questions about fatigue, pain, swelling and stiffness [18, 19]. ASDAS was developed to measure disease activity in patients with AS and contains questions about pain, swelling, stiffness, disease activity and inflammation [20].

For all these measures, a higher value indicates higher disease activity.

Functional ability

The Health Assessment Questionnaire Disability Index (HAQ-DI) and the Bath Ankylosing Spondylitis Functional Index (BASFI) measure functional ability through questions about mobility, daily activities, and self-care [19, 21]. For both scales, a higher value indicates more problems with functional ability.

VAS questions

The SRQ also contains three questions about pain, fatigue, and general health (global score), measured on a VAS. The questions ask how much pain the person has had, how fatigue they have been and how their general health has been in the last week due to their rheumatic disease. The scale ranges from no problem (0) to as bad as it can be (100) [22].

Hypotheses

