- Disease activity measured with DAS28/DAPSA/BASDAI/ASDAS and EQ-5D-3L **mobility**: a moderate positive correlation is expected.
- Disease activity measured with DAS28/DAPSA/BASDAI/ASDAS and EQ-5D-3L **self-care**: a moderate positive correlation is expected.
- Disease activity measured with DAS28/DAPSA/BASDAI/ASDAS and EQ-5D-3L **daily activities**: a moderate positive correlation is expected.
- Disease activity measured with DAS28/DAPSA/BASDAI/ASDAS and EQ-5D-3L **pain/discomfort**: a moderate positive correlation is expected.

HAQ-DI/BASFI

- Functional ability measured with HAQ-DI/BASFI and EQ-5D-3L **index**: a moderate negative correlation is expected.
- Functional ability measured with HAQ-DI/BASFI and EQ-5D-3L **mobility**: a moderate positive correlation is expected.
- Functional ability measured with HAQ-DI/BASFI and EQ-5D-3L **self-care**: a moderate positive correlation is expected.

Karolinska Institutet – Research protocol: Follow-up with patient-reported outcome measures for improved health related quality of life – Construct validity and responsiveness of EQ-5D-3L in patients with rheumatic disease

- Functional ability measured with HAQ-DI/BASFI and EQ-5D-3L **daily activities**: a moderate positive correlation is expected.
- Functional ability measured with HAQ-DI/BASFI and EQ-5D-3L **pain/discomfort**: a moderate positive correlation is expected.

Known-groups validity EQ-5D-3L

In the assessment of known-groups validity, patients will be divided into groups for which there is an expected difference in HRQoL. The groups represent patients with different levels of disease activity or functional ability. Patients with lower disease activity (<3.2 measured with DAS28, <14 measured with DAPSA, <2.1 measured with ASDAS and <4 measured with BASFI) are expected to have better health and HRQoL compared to patients with higher disease activity (≥ 3.2 measured with DAS28, >14 measured with DAPSA, ≥ 2.1 measured with ASDAS and ≥ 4 measured with BASDAI). Likewise, patients with better functional ability (<1 measured with HAQ-DI and <4 measured with BASFI) are expected to have better health and HRQoL compared to patients with worse functional ability (≥ 1 measured with HAQ-DI and ≥ 4 measured with BASFI). The cut off values for disease activity (DAS28 [23], DAPSA [24], ASDAS [25, 26], BASDAI [25–27]) and functional ability (HAQ-DI [28, 29], BASFI [27]) were taken from the literature.

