- More reported problems in EQ-5D-3L **daily activities** are expected in patients with high/very high disease activity compared to patients

Karolinska Institutet – Research protocol: Follow-up with patient-reported outcome measures for improved health related quality of life – Construct validity and responsiveness of EQ-5D-3L in patients with rheumatic disease

with inactive disease/low disease activity.

- More reported problems in EQ-5D-3L **pain/discomfort** are expected in patients with high/very high disease activity compared to patients with inactive disease/low disease activity.

BASDAI

- Lower EQ-5D-3L **index** values are expected in patients with high disease activity compared to patients with low disease activity.
- More reported problems in EQ-5D-3L **mobility** are expected in patients with high disease activity compared to patients with low disease activity.
- More reported problems in EQ-5D-3L **self-care** are expected in patients with high disease activity compared to patients with low disease activity.
- More reported problems in EQ-5D-3L **daily activities** are expected in patients with high disease activity compared to patients with low disease activity.
- More reported problems in EQ-5D-3L **pain/discomfort** are expected in patients with high disease activity compared to patients with low disease activity.

BASFI/HAQ-DI

- Lower EQ-5D-3L **index** values are expected in patients with less functional ability compared to patients with more functional ability.
- More reported problems in EQ-5D-3L **mobility** are expected in patients with less functional ability compared to patients with more functional ability.
- More reported problems in EQ-5D-3L **self-care** are expected in patients with less functional ability compared to patients with more functional ability.

Karolinska Institutet – Research protocol: Follow-up with patient-reported outcome measures for improved health related quality of life – Construct validity and responsiveness of EQ-5D-3L in patients with rheumatic disease

functional ability.

- More reported problems in EQ-5D-3L **daily activities** are expected in patients with less functional ability compared to patients with more functional ability.
- More reported problems in EQ-5D-3L **pain/discomfort** are expected in patients with less functional ability compared to patients with more functional ability.

Responsiveness EQ-5D-3L

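### The lower-disease-activity cut-off for ankylosing spondylitis names BASFI where the higher one names BASDAI, so the BASDAI known-groups comparison is not a valid split as written

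*Combined protocol and SAP*

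**What the plan says.** Under Known-groups validity EQ-5D-3L, "patients will be divided into groups for which there is an expected difference in HRQoL". One sentence then sets the disease-activity cut-offs. The lower-activity list ends "<2.1 measured with ASDAS and <4 measured with BASFI) are expected to have better health and HRQoL compared to patients with higher disease activity". The higher-activity list ends ">14 measured with DAPSA, ≥ 2.1 measured with ASDAS and ≥ 4 measured with BASDAI". The following sentence defines the functional-ability groups, with the better group given as "<1 measured with HAQ-DI and <4 measured with BASFI" and the worse group as the complement. The sources are then listed by construct. BASDAI closes the disease-activity sources and BASFI is placed with function: "BASDAI [25–27]) and functional ability (HAQ-DI [28, 29], BASFI [27]) were taken from the literature".

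The Outcome measures section keeps the two instruments apart. Under Disease activity, "BASDAI was developed to measure disease activity in patients with AS". Under Functional ability, the HAQ-DI and the "Bath Ankylosing Spondylitis Functional Index (BASFI) measure functional ability".

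The hypotheses that use the split stand under a BASDAI heading. For the index and four dimensions the contrast is between high and low disease activity; for the index, lower "values are expected in patients with high disease activity compared to patients with low disease activity". Known-groups validity EQ VAS adopts the same groups and adds one BASDAI hypothesis.

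**The concern.** A known-groups comparison needs each patient to be in exactly one group, and both groups to be defined on the characteristic they are supposed to differ in. The printed AS rule meets neither requirement, because the better group is defined on function and the worse group on disease activity.

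Three things would follow if the text were applied as it stands:

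- The BASDAI and BASFI comparisons would share the same better group (BASFI <4), so they would not be separate tests.
- The protocol describes BASFI as asking about mobility, daily activities and self-care. Three of the five affected EQ-5D-3L hypotheses concern those dimensions, so the better group would be selected on closely related content.
- AS patients must have BASDAI to be included, but not BASFI. An eligible patient without a BASFI value could never enter the lower group.

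The hypotheses are declared a priori and count towards the rule that 75% must be supported in each patient group. Their group definitions should therefore be right in the written plan and not depend on the analyst noticing an error.

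**Working it through.** **Step 1. Are the printed cut-off pairs complementary?** All are from Known-groups validity EQ-5D-3L.

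| Instrument | Better side | Worse side | Complementary? |
|---|---|---|---|
| DAS28 | <3.2 | ≥3.2 | yes |
| DAPSA | <14 | >14 | no, 14 is unassigned |
| ASDAS | <2.1 | ≥2.1 | yes |
| BASDAI | none printed (BASFI <4 in its place) | ≥4 | no |
| HAQ-DI (function) | <1 | ≥1 | yes |
| BASFI (function) | <4 | ≥4 | yes |

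**Step 2. Where does the literal AS rule put each patient?** Lower group = BASFI <4; higher group = BASDAI ≥4.

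| BASDAI | BASFI | Literal rule | BASDAI on both sides |
|---|---|---|---|
| <4 | <4 | lower only | lower |
| <4 | ≥4 | neither | lower |
| ≥4 | <4 | both | higher |
| ≥4 | ≥4 | higher only | higher |

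Two of the four combinations are assigned once, one twice and one not at all. With BASDAI on both sides, every patient with a BASDAI value is assigned exactly once. The number of patients in the two misassigned cells cannot be computed, because the protocol gives no joint distribution of BASDAI and BASFI.

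**Step 3. Which instrument was meant?** Four parts of the protocol agree on BASDAI: the construct definitions under Outcome measures, the source list for the cut-offs, the separate BASFI <4 / ≥4 pair for function, and the BASDAI headings over the hypotheses for both EQ-5D-3L and EQ VAS. None supports BASFI as a disease-activity measure. No other section prints a lower BASDAI cut-off.

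**Step 4. How many AS hypotheses use the split?** Bullets are counted as printed, assuming that AS uses BASFI and not HAQ-DI for function.

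- EQ-5D-3L known-groups: ASDAS 5 + BASDAI 5 + BASFI 5 = 15. Affected: 5/15 = 33.3%.
- EQ-5D-3L convergent: 5 + 1 + 5 + 5 + 5 = 21. With known-groups, 21 + 15 = 36; 5/36 = 13.9%.
- EQ-5D-3L responsiveness: 21 correlations + 2 AUC = 23. All together, 36 + 23 = 59; 5/59 = 8.5%.
- EQ VAS: known-groups 3, convergent 5, responsiveness 5 + 2 = 7. Affected: 1/3 = 33.3%, 1/8 = 12.5%, 1/15 = 6.7%.

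Several denominators are shown because the protocol does not say whether the 75% rule applies to each property or to all hypotheses pooled. Two counting choices change the figures:

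- The pooled counts above treat BASDAI and ASDAS as one bullet outside known-groups. Counted separately, the EQ-5D-3L totals become 26 + 15 = 41 and 41 + 29 = 70 (12.2% and 7.1%). The EQ VAS totals become 6 + 3 = 9 and 9 + 9 = 18 (11.1% and 5.6%).
- If HAQ-DI is also tested separately in AS, the known-groups shares become 5/20 = 25% and 1/4 = 25%.

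**Step 5. What does the 75% rule then require?** If it is applied to known-groups alone, with BASFI only: 0.75 × 15 = 11.25, so 12 of 15 EQ-5D-3L hypotheses must be supported. At most 3 may fail, and 5 depend on this split. For EQ VAS, 0.75 × 3 = 2.25, so all 3 must be supported. If the rule is pooled, the affected share is smaller.

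**The case against.** The strongest reply is that this is a clerical error with only one sensible reading. The higher side is printed correctly, the heading says BASDAI, and the value 4 agrees on both sides, so only the instrument label is wrong. The literal rule cannot be coded as a single two-level variable, so an analyst would probably notice. The percentages count hypotheses that use the split, not hypotheses whose result would change, and they depend on a pooling unit and a choice of functional measure that the protocol leaves open. The DAPSA gap is a separate matter and adds no weight to the BASFI error.

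Most of this stands. The intended reading can be recovered, the percentages measure scope and not impact, and the DAPSA point is minor. It does not remove the need for a correction. This sentence is the only numeric definition of the groups. An analyst who silently uses BASDAI departs from the written plan, and one who follows the text obtains overlapping and incomplete groups.

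**Conclusion.** The concern holds. The lower-disease-activity cut-off for AS names the wrong instrument, and as written the rule is neither mutually exclusive nor exhaustive. That BASDAI <4 was meant is an inference, but a well-supported one.

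The scope is limited to AS and to six known-groups hypotheses, five for EQ-5D-3L and one for EQ VAS. Convergent validity, responsiveness, and the rheumatoid arthritis and polyarthritis analyses are untouched by the BASFI/BASDAI mismatch. No changed conclusion is claimed. It should be corrected before analysis because it is an operative rule and the correction is trivial.

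The DAPSA gap is real but minor. It concerns only scores of exactly 14, in an unknown number of patients, and the group labels (remission/low against moderate/high) show that no level was meant to be left out.

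**What to change.** Under Known-groups validity EQ-5D-3L, replace BASFI with BASDAI in the lower-disease-activity list, so that the comparison is BASDAI <4 against BASDAI ≥4. Keep BASFI <4 against ≥4 for functional ability only. The EQ VAS groups follow automatically. Record the correction with a date before the analysis starts.

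At the same time, make one of the two DAPSA inequalities inclusive, with the authors assigning a score of 14 according to the source they cite for that cut-off (reference 24).

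The cost is one word and one inequality sign. No extra data are needed, since BASDAI is already required for AS patients to be included.

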The analyses will be conducted independently for the different patient groups. To support construct validity and responsiveness of EQ-5D-3L and EQ VAS in each patient group, 75% of the hypotheses will need to be supported [6–9]. Historical registry data from the Swedish Rheumatology Register (SRQ) will be used to assess the construct validity and responsiveness of EQ-5D-3L and EQ VAS. Data on EQ-5D-3L has been collected since 2008 [10] and the study will include data from 2008 until the time of data extraction.

Ethical approval has been granted for the project (2023-04394-01).

Karolinska Institutet – Research protocol: Follow-up with patient-reported outcome measures for improved health related quality of life – Construct validity and responsiveness of EQ-5D-3L in patients with rheumatic disease

Study population

Inclusion criteria are:

- 18 years and older at the time of first included measurement
- A diagnosis of RA, polyarthritis, PsA, or AS
- Complete registration of responses in the EQ-5D-3L descriptive system or EQ VAS on at least one time point in SRQ
- For patients with RA: At least one measurement with Disease Activity Score 28 (DAS28) reported in relation to the same visit as EQ-5D-3L
- For patients with polyarthritis: At least one measurement with DAS28 reported in relation to the same visit as EQ-5D-3L
- For patients with PsA: At least one measurement with DAS28 or Disease Activity in Psoriatic Arthritis (DAPSA) reported in relation to the same visit as EQ-5D-3L
- For patients with AS: At least one measurement with the Bath Ankylosing Spondylitis Disease Activity Index (BASDAI) reported in relation to the same visit as EQ-5D-3L

For the analyses of construct validity, the latest measurement will be used if the individual patients have multiple complete registrations with EQ-5D-3L and the other required measure. The hypotheses for responsiveness will be tested in patients with newly diagnosed disease (having the diagnosis for ≤ 12 months), as changes in disease activity are likely to be present in this group. For the analysis of responsiveness, the two first measurements during the first year will be used.

Outcome measures

EQ-5D-3L and EQ VAS

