To assess the magnitude of the differences in the proportions of reported problems in the EQ-5D-3L dimensions between groups, the effect size (r) will be calculated. The effect size is considered small if it is ≥ 0.1 , medium if it is ≥ 0.3 and large if it is ≥ 0.5 [30–32]. To support the hypotheses for the dimensions, at least a small effect size will be required.

To estimate whether there is a difference in the EQ-5D-3L mean index value between groups, cut-off values for minimally important differences (MID) will be used. Minimal important differences represent the smallest improvement considered worthwhile by a patient [33]. The MID values used in this study will be based on the literature.

The hypotheses for known-groups validity of EQ-5D-3L are presented in the text below.

Karolinska Institutet – Research protocol: Follow-up with patient-reported outcome measures for improved health related quality of life – Construct validity and responsiveness of EQ-5D-3L in patients with rheumatic disease

DAS28/DAPSA

- Lower EQ-5D-3L **index** values are expected in patients with moderate/high disease activity compared to patients in remission/with low disease activity.
- More reported problems in EQ-5D-3L **mobility** are expected for patients with moderate/high disease activity compared to patients in remission/with low disease activity.
- More reported problems in EQ-5D-3L **self-care** are expected for patients with moderate/high disease activity compared to patients in remission/with low disease activity.
- More reported problems in EQ-5D-3L **daily activities** are expected for patients with moderate/high disease activity compared to patients in remission/with low disease activity.
- More reported problems in EQ-5D-3L **pain/discomfort** are expected for patients with moderate/high disease activity compared to patients in remission/with low disease activity.

ASDAS

- Lower EQ-5D-3L **index** values are expected in patients with high/very high disease activity compared to patients with inactive disease/low disease activity.
- More reported problems in EQ-5D-3L **mobility** are expected in patients with high/very high disease activity compared to patients with inactive disease/low disease activity.
- More reported problems in EQ-5D-3L **self-care** are expected in patients with high/very high disease activity compared to patients with inactive disease/low disease activity.

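### Does the undefined effect size r leave the verdict on the EQ-5D-3L known-groups dimension hypotheses open?

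*Combined protocol and SAP*

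**What the plan says.** The protocol section on known-groups validity of EQ-5D-3L states that, to judge the size of "the differences in the proportions of reported problems in the EQ-5D-3L dimensions between groups, the effect size (r) will be calculated". It then sets the scale: "The effect size is considered small if it is ≥ 0.1 , medium if it is ≥ 0.3", and large from 0.5. The pass mark follows: "To support the hypotheses for the dimensions, at least a small effect size will be required". References 30 to 32 are cited for the scale.

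The section on EQ-5D-3L and EQ VAS gives three ordered answers per dimension: "no problem (1), some/moderate problem (2) unable to perform certain activities/having extreme problems (3").

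Each of the four known-groups blocks (DAS28/DAPSA, ASDAS, BASDAI, BASFI/HAQ-DI) lists one index hypothesis and four dimension hypotheses. The index is judged differently: "cut-off values for minimally important differences (MID) will be used". The dimension hypotheses are directional, for example "More reported problems in EQ-5D-3L pain/discomfort are expected in patients with less functional ability compared to patients with more functional ability".

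Under study design and data collection, the overall rule for each patient group is that "75% of the hypotheses will need to be supported".

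**The concern.** A numerical pass mark fixes a decision only if the statistic is fixed. Here r could be phi on a 2×2 table, z/√N from a Mann-Whitney test on three levels, or a rank-biserial r. These differ in two ways. Phi on any problem versus none does not see a shift from level 2 to level 3, while the rank versions do. The rank-biserial r also scales differently with the base rate and the group balance.

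The registry data already exist and the hypotheses are described as a priori. An analyst who chose the formula after seeing the counts could move a dimension across 0.1. Sixteen of the 20 listed EQ-5D-3L known-groups hypotheses rest on r, so the 75% verdict could in principle move with them. Pain/discomfort looks most exposed (most patients report something, and groups may differ mainly in extreme problems), followed by self-care (few report problems).

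**Working it through.** The plan gives no expected proportions, group sizes or value of r, so there is no figure to reproduce. All counts below are assumptions, written as level 1/2/3, better group versus worse group.

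**Formulas.** Let p₁ and p₂ be the proportions with any problem, p the pooled proportion and f the share of patients in the worse group.
- phi = (p₂ − p₁)·√[f(1 − f)/(p(1 − p))].
- z/√N, with z = (U − n₁n₂/2)/√V and V = (n₁n₂/12)·[(N + 1) − Σ(t³ − t)/(N(N − 1))], where t are the pooled level counts.
- Rank-biserial = 2U/(n₁n₂) − 1.

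**Pain/discomfort, 140/525/35 vs 36/189/75 (N = 1000).**
- phi = (0.88 − 0.80)·√[0.21/(0.824·0.176)] = 0.096.
- U = 36·70 + 189·402.5 + 75·682.5 = 129,780. Rank-biserial = 259,560/210,000 − 1 = 0.236.
- V = 17,500·(1001 − 371.15), so √V ≈ 3,320. z = 24,780/3,320 = 7.46, and z/√N = 0.236.

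**All tables, same formulas.**

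| Counts | phi | z/√N, 3 levels, tie-corrected | rank-biserial |
|---|---|---|---|
| 140/525/35 vs 36/189/75 | 0.096 | 0.236 | 0.236 |
| 140/525/35 vs 39/216/45 | 0.084 | 0.152 | 0.147 |
| 200/770/30 vs 180/680/140 | 0.025 | 0.119 | 0.107 |
| 658/39/3 vs 258/39/3 | 0.132 | 0.132 | 0.080 |
| 950/45/5 vs 890/105/5 | 0.111 | 0.110 | 0.060 |
| 1260/520/20 vs 118/78/4 | 0.071 | 0.072 | 0.111 |
| 900/95/5 vs 650/330/20 | 0.299 | 0.299 | 0.250 |

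Opposite verdicts at 0.1 therefore exist. Four checks show how much they matter.

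**1. What the text supports.** The plan speaks of proportions reporting problems, and each hypothesis speaks of more problems being reported. Both point to any problem versus none. On that coding tie-corrected z/√N equals phi·√[(N − 1)/N]. With 5% versus 11% and 1,000 per group, both are 0.1106 to four decimals. Two of the three candidates become one.

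**2. Which rows need another reading.** In the last four rows phi and z/√N give the same verdict. The fourth, fifth and sixth rows split only through rank-biserial r, which on a 2×2 table is just p₂ − p₁ (0.14 − 0.06 = 0.08 in the fourth). Nothing in the plan names it. The first three rows split only if three levels are kept.

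**3. How special the pain tables are.** In the first table the odds ratio for any problem is (0.88/0.12)/(0.80/0.20) = 1.8, and for extreme problems (0.25/0.75)/(0.05/0.95) = 6.3. The group difference sits almost wholly at level 3. In a latent bivariate normal model with the same margins (82.4% any problem, 11% extreme, 30% in the worse group), a z/√N of about 0.236 goes with a phi of about 0.17, which passes. In that model, where phi is 0.098, z/√N is 0.127.

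**4. What the plan expects.** The convergent hypotheses expect correlations of at least 0.3 between disease activity or function and these same four dimensions. In the latent-normal model (Spearman assumed, since no coefficient is named; 10–90% reporting problems; 20–50% in the worse group), r = 0.1 is reached at a correlation of 0.120–0.241 for phi, 0.120–0.140 for z/√N and 0.110–0.206 for rank-biserial. All are below 0.3. At 0.30 the ranges are phi 0.118–0.285, z/√N 0.214–0.285 and rank-biserial 0.143–0.279, so all pass.

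**Effect on the 75% rule, RA, taking HAQ-DI as the functional measure.** Known-groups: 2 blocks × 5 = 10, of which 8 rest on r. Convergent: 5 + 1 + 5 + 5 + 5 = 21.
- Pooled within construct validity: 75% of 31 = 23.25, so 24 are needed. If the rest are supported, 7 reversals leave 24 and only all 8 (leaving 23) change the result.
- Known-groups counted alone: 75% of 10 = 7.5, so 8 are needed, and 3 reversals leave 7.

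**The case for a change.** The best argument for acting is that a rule meant to be fixed in advance should not depend on a choice made with the data open, and that a sentence before extraction would settle it at no cost. The symbol r together with a 0.1/0.3/0.5 scale does fit a rank-based z/√N on the three ordered levels, so that reading is not far-fetched. For pain/discomfort a difference confined to extreme problems is clinically plausible, and phi would miss it. There is also a corner where the formulas part even at a correlation of 0.30: with 90% reporting problems and 10% in the worse group, phi is 0.088 and z/√N 0.184. Omitting the tie correction would cut z/√N in the fourth table from 0.132 to 0.064. If other hypotheses fail, fewer reversals are needed to cross 75%.

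Part of this stands. The formula and the coding are not in the protocol text, and weak contrasts can go either way. The cited references may define r, but they cannot be consulted here and nothing rests on them. What does not follow is that a sensible analyst would reach an unsound answer. Phi on any versus no problem follows the wording but ignores level 3. Three-level z/√N keeps level 3 but is not a difference in proportions. Neither is clearly better. Dropping the tie correction with only three response levels is not a reasonable option. Separate counts for convergent and known-groups validity are a different reporting question. The plan presents the two as the two parts of construct validity, so pooling is the plainer reading.

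**Conclusion.** No change to the plan follows. The gap is real but is one of written detail. On the reading the text best supports, phi and tie-corrected z/√N give the same verdict, apart from values that practically equal 0.1. A three-level r gives a different verdict only for weak contrasts, or where groups differ chiefly in extreme problems. If the plan's own expectation of correlations of at least 0.3 holds, all three versions pass within the range examined, the lowest value being 0.118. For RA, with the tally pooled and everything else supported, all 8 dimension hypotheses would have to reverse before the conclusion changed. On separate counting it would take 3.

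This rests on assumed response distributions and group shares, a latent-normal model, Spearman correlation, and HAQ-DI as the functional measure in RA. The documents do not allow a count of how many pairs lie near 0.1, so the effect on the 75% result is judged small rather than shown to be nil.
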